6.1.2 ADMINISTRATION AND/OR DOSING

The intervention is delivered by trained exercise coaches.

6.2 FIDELITY

6.2.1 INTERVENTIONIST TRAINING AND TRACKING

We will test coach and research personnel training as part of our feasibility objective.

6.3 MEASURES TO MINIMIZE BIAS: RANDOMIZATION AND BLINDING

Participants are randomized to intervention or usual care using a random number generator in a 1:1 intervention to control fashion. Due to funding restraints we are not using blinded data collectors for this pilot feasibility study.

6.4 STUDY INTERVENTION/EXPERIMENTAL MANIPULATION ADHERENCE

Adherence to exercise is a secondary outcome.

6.5 CONCOMITANT THERAPY

6.5.1 RESCUE THERAPY

N/A

7 STUDY INTERVENTION/EXPERIMENTAL MANIPULATION DISCONTINUATION AND PARTICIPANT DISCONTINUATION/WITHDRAWAL

7.1 DISCONTINUATION OF STUDY INTERVENTION/EXPERIMENTAL MANIPULATION

If patients are unable to safely complete the CPET or if their CPET results indicate they exceed our thresholds for cardiorespiratory fitness, they will be immediately withdrawn from the study. If the patient withdraws consent, the patient will be removed from the research study..

When a subject discontinues from HEART Camp Connect but not from the study, remaining study procedures will be completed as indicated by the study protocol. If a clinically significant finding is identified (including, but not limited to changes from baseline) after enrollment, the investigator or qualified designee will determine if any change in participant management is needed. Any new clinically relevant finding will be reported as an adverse event (AE).

7.2 PARTICIPANT DISCONTINUATION/WITHDRAWAL FROM THE STUDY

Participants are free to withdraw from participation in the study at any time upon request.

An investigator may discontinue a participant from the study for the following reasons:

- Significant study intervention non-compliance, unless varying compliance is an aspect of the study objectives
- Lost-to-follow up; unable to contact subject (see **Section 7.3, Lost to Follow-Up**)
- Any event or medical condition or situation occurs such that continued collection of follow-up study data would not be in the best interest of the participant or might require an additional treatment that would confound the interpretation of the study
- The participant meets an exclusion criterion (either newly developed or not previously recognized) that precludes further study participation
-

The reason for participant discontinuation or withdrawal from the study will be recorded. Subjects who sign the informed consent form and are randomized but do not receive the study intervention may be replaced. Subjects who sign the informed consent form, and are randomized and receive the study intervention, and subsequently withdraw, or are discontinued from the study, will not be replaced.

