6.1.1 STUDY INTERVENTION

The HEART Camp Connect intervention is founded in social-cognitive theory⁴⁶ and the future-oriented motivation and self-regulation model proposed by Miller and Brickman.⁴⁷ HEART Camp Connect (n=25) includes weekly virtual coaching sessions with experienced coaches from Engage. For 3 weeks per month, coaches and participants meet 1-on-1 via videoconference to review heart rate data, exercise diaries from the prior week and initiate discussion related to behavioral change mechanisms. One week per month HEART Camp Connect participants will be assigned to a small group (1 coach:5 participants) exercise/observation session. During these sessions, coaches will demonstrate exercises and observe participants via videoconference for proper form and real-time encouragement in a group setting. Coaches will call any HEART Camp Connect participant that fails to

attend their scheduled weekly coaching session for 2 consecutive weeks. Participants achieving a minimum of 120 minutes of moderate-intensity exercise per week on average weeks 1-12 will be given the option to opt-out of coaching sessions for weeks 13-16. We recognize that this could potentially create variation in the dose of the coaching and therefore, will closely monitor the minutes of coaching per participant throughout the study. We will also closely monitor adherence during this time. Participants that relapse (become non-adherent for 2 consecutive weeks) for any reason (e.g., hospitalization, loss of motivation) will return to weekly coaching for the remainder of the intervention. Testing optional coaching is part of our feasibility assessment and increases the future scalability of this intervention. In the sustainability period (Weeks 17-24), weekly coaching stops, and HEART Camp Connect participants are expected to self-regulate exercise and maintain adherence.

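### Section 7.2 permits the investigator to end a participant's follow-up for reasons that can be related to outcome, and section 9 sets no all-randomised summary to offset the loss

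*Combined protocol and SAP*

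**What the plan says.** Protocol section 7.2 introduces its list with "An investigator may discontinue a participant from the study for the following reasons". Two of the grounds matter here:

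- "Significant study intervention non-compliance, unless varying compliance is an aspect of the study objectives".
- An event, condition or situation that makes further data collection contrary to the participant's interest, or that "might require an additional treatment that would confound the interpretation of the study".

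The section also requires the reason for each exit to be recorded, and it sets a replacement rule: "Subjects who sign the informed consent form and are randomized but do not receive the study intervention may be replaced". Those who received the intervention and then left are not replaced.

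Section 7.1 covers the lesser step of stopping coaching alone: "When a subject discontinues from HEART Camp Connect but not from the study, remaining study procedures will be completed as indicated by the study protocol". Section 6.1.1 says that coaching participants who relapse "for any reason (e.g., hospitalization, loss of motivation) will return to weekly coaching". Section 6.4 states: "Adherence to exercise is a secondary outcome".

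On analysis, section 9.3 defines no population, and section 9.4 plans descriptive summaries only, with no rule for missing data. Retention is named as a feasibility measure in section 2.1, and feasibility is the primary endpoint (sections 3 and 9.1), but no numerator or denominator is given. Section 6.3 states that data collectors are not blinded.

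**The concern.** Taking someone out of the study ends their outcome data, whereas stopping coaching does not. A change in treatment can reflect worsening health, and poor compliance can go with little exercise. If follow-up ends for such reasons, the participants still measured at Week 12 and Week 24 are a selected group, and a simple mean over them does not describe the arm as randomised.

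A change of treatment is foreseeable. Section 5.1 asks for only 30 days of stable drug therapy, follow-up runs to Week 24 (section 1.3), and section 2.2 describes drug treatment for this condition as still developing. The protocol does not say what would count as confounding, so the decision is discretionary. Nothing says that the person deciding is unaware of the assigned arm.

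Two results are exposed: mean exercise minutes per week by arm (the secondary endpoint) and retention (part of the primary endpoint). In a descriptive pilot meant to support a funding application, these summaries are the whole result.

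**Working it through.** The plan states no expected mean, standard deviation, dropout rate or power, so there is no figure of its own to reproduce. What follows is an illustration.

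**Inputs from the protocol.** Total enrolment is 25 (section 1.1) and allocation is 1:1 (section 6.3), so 12 or 13 per arm. Section 6.1.1 instead gives 25 for the coaching arm, which does not fit 25 in total at 1:1 and needs reconciling; I show it as a third case. The figure of 120 min/week is the opt-out threshold in section 6.1.1, borrowed here as a benchmark.

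**Assumptions.** Those kept average 120 min/week, those removed average *m* = 0 to 60, and *k* = 1 to 3 are removed from an arm of *n*.

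**Mean minutes.** The mean over everyone randomised to the arm is [(n − k) × 120 + k × m] / n. The mean over those kept is 120. The overstatement is therefore k × (120 − m) / n.

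| Removed (k) | n = 12 | n = 13 | n = 25 |
|---|---|---|---|
| 1 | 5.0 to 10.0 | 4.6 to 9.2 | 2.4 to 4.8 |
| 2 | 10.0 to 20.0 | 9.2 to 18.5 | 4.8 to 9.6 |
| 3 | 15.0 to 30.0 | 13.8 to 27.7 | 7.2 to 14.4 |

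The low end of each range is m = 60 and the high end m = 0. For example, with n = 13, k = 3 and m = 0, the full mean is (10 × 120 + 3 × 0) / 13 = 92.3, against 120 observed, a gap of 27.7.

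**Less stark selection.** A simulation used minutes centred on 100, SD 40 or 60, floored at zero, with n = 13 and three removed. The arm mean rose by 14.6 to 20.9 when the lowest three were removed, and by 9.7 to 14.2 when three were drawn at random from the lower half.

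**When the error vanishes.** If removal is unrelated to minutes, the expected error is zero. If removal acts equally in both arms, the error cancels in the between-arm difference, although each arm's own mean is still shifted.

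**Retention.** With three of 13 removed, retention is 10/13 = 76.9% if they count as losses and 10/10 = 100% if they leave the denominator. The protocol does not say which applies.

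**The case against.** A reader might infer that section 7.2 removes poor outcomes, mostly from the coaching arm. The documents do not support that.

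- The wording is permissive, so no removal is certain.
- The additional-treatment ground applies equally to both arms.
- Only the non-compliance ground is specific to coaching, and its own exception probably switches it off. Section 2.2 says attendance at coaching is monitored. Section 3 puts fidelity and acceptability in the primary endpoint. Section 6.1.1 expects the coaching dose to vary, tracks it, and makes optional coaching part of the feasibility question. It answers two consecutive missed sessions with a call from the coach. One can argue that section 6.4 names adherence to exercise and not to coaching, and that the opt-out covers only weeks 13 to 16. That leaves the exception unclear, but it is the weaker reading.

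A reader might also see a contradiction with sections 7.1 and 6.1.1. Sections 7.1 and 7.2 describe two tiers: leaving coaching, and leaving the study. The relapse rule in 6.1.1 follows the opt-out text, fits best those who opted out, and does not address study discontinuation.

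Nor can retention be said to be biased in a known direction. Because reasons for exit are recorded, investigator-initiated exits could be reported separately. Finally, there is no inferential analysis, so no test or power figure is affected.

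All of this stands. It narrows the point but does not remove it: the additional-treatment ground remains active, and nothing in section 9 compensates for the data lost.

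**Conclusion.** The concern holds as a risk. Section 7.2 allows follow-up to be ended for additional treatment, and for non-compliance if its exception is read as not applying. Either reason can be related to outcome. With 13 in an arm, one to three removals would overstate mean minutes by about 5 to 28 min/week, resting wholly on the assumed 120 min/week for those kept and 0 to 60 for those removed. The error averages zero if removal is unrelated to minutes. The documents do not show how often removal would happen, in which arm, or which way retention would move; 77% and 100% are both possible for three removals. The consequence is modest in a descriptive pilot, but the remedy is cheap and the change is worth making.

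**What to change.** In section 7.2:

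1. Delete the non-compliance bullet, and delete the clause "might require an additional treatment that would confound the interpretation of the study" (with the conjunction before it), as grounds for ending follow-up.
2. State that Week 12 and Week 24 data are collected on every randomised participant unless consent is withdrawn, the participant cannot be reached, or continued data collection is against the participant's interest. The last ground is already in 7.2 and must be kept.
3. Reconcile the bullet on a newly met exclusion criterion with that sentence.

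In section 9, summarise by assigned arm, put all randomised participants in the retention denominator, and report investigator-initiated exits by arm and reason, with any replacements shown.

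Decisions about care and about continuing coaching stay with the investigator under section 7.1.

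The cost is two deletions and a few sentences. No visits are added, because section 1.3 already schedules both assessments; the only extra work is completing them for participants who would otherwise have been discontinued.

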7.3 LOST TO FOLLOW-UP

A participant will be considered lost to follow-up if he or she fails to return for 2 scheduled visits and study staff are unable to contact the participant after at least 3 attempts.

The following actions must be taken if a participant fails to return to the clinic for a required study visit:

- The site will attempt to contact the participant, reschedule the missed visit <specify time frame>, counsel the participant on the importance of maintaining the assigned visit schedule and ascertain if the participant wishes to and/or should continue in the study
- Before a participant is deemed lost to follow-up, the investigator or designee will make every effort to regain contact with the participant (where possible, 3 telephone calls and, if necessary, a certified letter to the participant's last known mailing address or local equivalent methods). These contact attempts will be documented in the participant's medical record or study file.
- Should the participant continue to be unreachable, he or she will be considered to have withdrawn from the study with a primary reason of lost to follow-up

8 STUDY ASSESSMENTS AND PROCEDURES

8.1 ENDPOINT AND OTHER NON-SAFETY ASSESSMENTS

Data monitoring will occur on an ongoing basis, weekly at a minimum, and in the event of Any adverse event the Data Safety monitor will be notified.

8.2 SAFETY ASSESSMENTS

Cardiopulmonary exercise testing is used a baseline safety evaluation.

8.3 ADVERSE EVENTS AND SERIOUS ADVERSE EVENTS

8.3.1 DEFINITION OF ADVERSE EVENTS

This protocol uses the definition of adverse event from 21 CFR 312.32 (a): any untoward medical occurrence associated with the use of an intervention in humans, ***whether or not considered intervention-related.***

8.3.2 DEFINITION OF SERIOUS ADVERSE EVENTS

The study will be stopped if any adverse events result in the necessity for emergency care. These events will be reported immediately to the IRB and closely investigated by study

personnel. If any death occurs as the result of exercise or within 3 hours of an exercise session, the study will be stopped.

8.3.3 CLASSIFICATION OF AN ADVERSE EVENT

8.3.3.1 SEVERITY OF EVENT

For adverse events (AEs) not included in the protocol defined grading system, the following guidelines will be used to describe severity.

- **Mild** – Events require minimal or no treatment and do not interfere with the participant's daily activities.
- **Moderate** – Events result in a low level of inconvenience or concern with the therapeutic measures. Moderate events may cause some interference with functioning.
- **Severe** – Events interrupt a participant's usual daily activity and may require systemic drug therapy or other treatment. Severe events are usually potentially life-threatening or incapacitating. Of note, the term "severe" does not necessarily equate to "serious".

8.3.3.2 RELATIONSHIP TO STUDY INTERVENTION/EXPERIMENTAL MANIPULATION

All adverse events (AEs) will have their relationship to study procedures, including the intervention, assessed by an appropriately-trained clinician based on temporal relationship and his/her clinical judgment. The degree of certainty about causality will be graded using the categories below.

- **Related** – The AE is known to occur with the study procedures, there is a reasonable possibility that the study procedures caused the AE, or there is a temporal relationship between the study procedures and the event. Reasonable possibility means that there is evidence to suggest a causal relationship between the study procedures and the AE.
- **Not Related** – There is not a reasonable possibility that the study procedures caused the event, there is no temporal relationship between the study procedures and event onset, or an alternate etiology has been established.

OR

- **Definitely Related** – There is clear evidence to suggest a causal relationship, and other possible contributing factors can be ruled out. The clinical event, including an abnormal laboratory test result, occurs in a plausible time relationship to study procedures administration and cannot be explained by concurrent disease or other drugs or chemicals. The response to withdrawal of the study procedures should be clinically plausible. The event must be pharmacologically or phenomenologically definitive.
- **Probably Related** – There is evidence to suggest a causal relationship, and the influence of other factors is unlikely. The clinical event, including an abnormal laboratory test result, occurs within a reasonable time after administration of the study procedures, is unlikely to be attributed to

concurrent disease or other drugs or chemicals, and follows a clinically reasonable response on withdrawal.

- **Potentially Related** – There is some evidence to suggest a causal relationship (e.g., the event occurred within a reasonable time after administration of study procedures). However, other factors may have contributed to the event (e.g., the participant's clinical condition, other concomitant events). Although an AE may rate only as "possibly related" soon after discovery, it can be flagged as requiring more information and later be upgraded to "probably related" or "definitely related", as appropriate.
- **Unlikely to be related** – A clinical event, including an abnormal laboratory test result, whose temporal relationship to study procedures administration makes a causal relationship improbable (e.g., the event did not occur within a reasonable time after administration of the study procedures) and in which other drugs or chemicals or underlying disease provides plausible explanations (e.g., the participant's clinical condition, other concomitant treatments).
- **Not Related** – The AE is completely independent of study procedures administration, and/or evidence exists that the event is definitely related to another etiology. There must be an alternative, definitive etiology documented by the clinician.]

8.3.3.3 EXPECTEDNESS

A clinician with appropriate expertise in heart failure will be responsible for determining whether an adverse event (AE) is expected or unexpected. An AE will be considered unexpected if the nature, severity, or frequency of the event is not consistent with the risk information previously described for the study procedures.

8.3.4 TIME PERIOD AND FREQUENCY FOR EVENT ASSESSMENT AND FOLLOW -UP

[The occurrence of an adverse event (AE) or serious adverse event (SAE) may come to the attention of study personnel during study visits and interviews of a study participant presenting for medical care, or upon review by a study monitor.

All AEs, not otherwise precluded per the protocol, will be captured on the appropriate case report form (CRF). Information to be collected includes event description, time of onset, clinician's assessment of severity, relationship to study procedures (assessed only by those with the training and authority to make a diagnosis), and time of resolution/stabilization of the event. All AEs occurring while on study will be documented appropriately regardless of relationship. All AEs will be followed to adequate resolution.

Any medical or psychiatric condition that is present at the time that the participant is screened will be considered as baseline and not reported as an AE. However, if the study participant's condition deteriorates at any time during the study, it will be recorded as an AE.

Changes in the severity of an AE will be documented to allow an assessment of the duration of the event at each level of severity to be performed. Documentation of onset and duration of each episode will be maintained for AEs characterized as intermittent.

<Insert role or name> will record events with start dates occurring any time after informed consent is obtained until 7 (for non-serious AEs) or 30 days (for SAEs) after the last day of study participation. At each study visit, the investigator will inquire about the occurrence of AE/SAEs since the last visit. Events will be followed for outcome information until resolution or stabilization.

8.3.5 ADVERSE EVENT REPORTING

The study will be stopped if any adverse events result in the necessity for emergency care. These events will be reported immediately to the IRB and closely investigated by study personnel. If any death occurs as the result of exercise or within 3 hours of an exercise session, the study will be stopped.

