1.3 SCHEDULE OF ACTIVITIES

	Pre-screening (Pre-consent)	Visit 1 Week 0	Visit 2 Week 12	Visit 3 – Final Week 24
EMR Review Eligibility	X			
Informed Consent		X		
Cardiopulmonary exercise test		X		
Demographics		X		
Clinical history		X	X	X
Height & Weight		X	X	X
Randomization		X		
Coaching Intervention*		*	*	*
Adverse Events Reporting		X	X	X
Feasibility Outcome Evaluations				
Recruitment and retention	X	X	X	X
Coach availability	X	X	X	X
Smart device availability	X	X	X	X
Connectivity issues	X	X	X	X
Patient Outcome Evaluation				
Intervention Acceptability				X
Pain Assessment (Brief Pain Inventory)		X	X	X
Quality of Life Questionnaire		X	X	X
Cognition		X	X	X
Health Status		X	X	X
Minutes of Exercise		X	X	X

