We advise all participants that they are under no obligation to respond to our questions and may decline to answer or stop at any time. Should a participant experience fatigue, we will allow them to take a break and continue or schedule another time within the next 48 hours to complete remaining questionnaires. If a subject responds to the symptom questionnaires that they have often or always felt depressed and/or hopeless in the past 7 days the researchers will refer them to their Primary Care Provider and provide a list of mental health resources including the Boys Town Grief Hotline. If upon questioning as to whether they have any plans to hurt themselves, they respond with a "yes" they will be immediately escorted to the Emergency Department or 9-1-1 will be contacted on their behalf.

Minimization of Risk of Exercise:

All participants will have successfully completed a cardiopulmonary exercise test (CPET). The results from the CPET will be used to develop an individualized exercise prescription for each participant that will guide heart rate parameters during exercise. Participants will be taught to monitor the intensity of their exercise by using heart rate and the rating of perceived exertion from their participation in our study orientation. We reduce the risk of exercising at home by requiring that another adult be present during the exercise in the event a subject experiences an adverse event requiring medical attention. The other adult will be instructed to contact the provider if the participant experiences a non-emergent adverse event or initiate local EMS, in the event of an emergency. The other adult will be instructed to then follow the instructions of the dispatcher. A list of potential adverse events that would warrant a call to a provider or EMS was attached to the application and will be shared with all participants. It is important to note that 150 minutes of moderate-intensity exercise is recommended for these patients and HFrEF patients are not eligible for cardiac rehabilitation. If these patients were not participating in this study, they could be doing this exercise on their own without the guidance that results from participating in this study.

Minimization of Risk of Loss of Confidentiality:

To protect against possible risks to confidentiality, research data will be stored in a locked

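### The study stops on any adverse event needing emergency care, yet no between-visit route or time limit is given for such an event to reach the study team

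*Combined protocol and SAP*

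**What the plan says.** - **Stopping rule (Section 8.3.5, repeated in 8.3.2).** "The study will be stopped if any adverse events result in the necessity for emergency care". The next sentence adds: "These events will be reported immediately to the IRB and closely investigated by study personnel".
- **Home events (Section 2.3.3).** Another adult must be present during home exercise. "The other adult will be instructed to contact the provider if the participant experiences a non-emergent adverse event or initiate local EMS", the latter for emergencies. All participants also receive a list of events that should prompt such a call. The section does not say that anyone tells the study team.
- **Active enquiry (Sections 8.3.4 and 1.3).** "At each study visit, the investigator will inquire about the occurrence of AE/SAEs since the last visit". The schedule is "Visit 1 Week 0 Visit 2 Week 12 Visit 3 – Final Week 24". Adverse-event reporting is marked at those three visits only, and record review at pre-screening only.
- **Passive routes (Section 8.3.4).** Staff may also learn of an event when a participant is interviewed while seeking medical care, or when a monitor reviews the study. The role that records events is an unfilled placeholder.
- **Monitoring (Section 8.1).** "Data monitoring will occur on an ongoing basis, weekly at a minimum", and the Data Safety monitor is told of any adverse event.
- **Coaching (Section 6.1.1).** The intervention arm has weekly sessions, with a call after two consecutive missed weeks. Participants averaging at least 120 minutes a week over Weeks 1-12 may opt out for Weeks 13-16. Adherence is watched during that time, and two non-adherent weeks bring them back to coaching. Then: "In the sustainability period (Weeks 17-24), weekly coaching stops".

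**The concern.** A rule triggered by one event anywhere in the study works only as fast as that event becomes known. Here the people who would know first, the participant and the other adult at home, are directed to the provider or EMS. The only scheduled question about adverse events comes at visits 12 weeks apart. An emergency at home could therefore meet the stopping criterion while the study carries on.

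Two things are at stake. Other participants could continue home exercise, for which Section 2.3.1 lists arrhythmia and death among the risks, after the condition for stopping has been met. Detection could also differ by arm: coached participants have weekly contact to Week 16, while no between-visit contact is described for controls. A simple comparison of event counts could then show more events with coaching only because more were heard about.

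**Working it through.** **1. The visit interval.** From Section 1.3, visits are at Weeks 0, 12 and 24. The gaps are 12 - 0 = 12 weeks and 24 - 12 = 12 weeks.

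**2. Which provisions shorten the wait?** Section 8.1's notice to the Data Safety monitor presupposes a known event. It does not say what the weekly monitoring reviews, and the Section 1.3 schedule shows no adverse-event item between visits. Section 8.3.6 allows 10 working days for a serious event, counted from when the investigator first learns of it, so it does not limit detection time. Coaching under Section 6.1.1 reviews heart rate data and exercise diaries and discusses behaviour. It could well reveal an event, but no adverse-event question or duty to forward one is written.

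**3. Wait under each assumption.** The longest wait is the largest gap between contacts assumed to reveal an event. The mean takes the event time as uniform over Weeks 0-24, so a gap of length g has mean wait g/2.

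| Contacts assumed to reveal an event | Longest wait (weeks) | Mean wait (weeks) |
|---|---|---|
| Visits only (controls as described) | 12 | 12/2 = 6.0 |
| Visits and weekly coaching to Week 16 | 24 - 16 = 8 | (16 x 0.5 + 8 x 4)/24 = 1.7 |
| Visits and weekly coaching to Week 12 (opt-out, adherence monitoring misses the event) | 24 - 12 = 12 | (12 x 0.5 + 12 x 6)/24 = 3.25 |
| Weekly monitoring captures adverse events | 1 | 0.5 |
| Week 12 visit missed, no other contact | 24 - 0 = 24 | 24/2 = 12.0 |

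The Week 16 end of coaching comes from Section 6.1.1. Section 1.1 describes a 3-month intervention. If coaching ended at Week 12, the third row would apply to the whole coached arm. The last row is a limiting case, since Section 7.3 requires contact attempts after a missed visit.

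**4. Others on study meanwhile.** The documents give no accrual rate. Participation is 24 weeks = 24 x 7/30.44 = 5.52 months. With even accrual of N people over A months, the number on study at once is N x 5.52/A:

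- N = 25, A = 18 (24-month study less 6 months of participation): 25 x 5.52/18 = 7.7
- N = 25, A = 12 (assumed): 25 x 5.52/12 = 11.5
- N = 50, A = 18: 50 x 5.52/18 = 15.3

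N = 50 is included because Section 6.1.1 gives n=25 for the intervention itself, which with the 1:1 allocation in Section 6.3 implies about 50, against 25 enrolled in Section 1.1. Under 1:1 allocation about half of any of these figures would be controls.

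**The case against.** The strongest case against is that the plan has more surveillance than the visit schedule shows. Coaches see intervention participants weekly to Week 16, read the previous week's diaries and telephone those who miss two weeks. Section 6.1.1 names hospitalization as a reason for relapse, so the plan expects to hear of such events. During the opt-out window adherence is watched, so an event that halts exercise could surface in about two weeks. The trial is single-site and recruits from its own clinics, and Section 8.3.4 lists two further routes. If coaching reveals events, the coached-arm mean wait is 1.7 weeks. If the weekly monitoring captures adverse events, the mean is about half a week.

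Much of this stands for coached participants up to Week 16. It does not help controls, for whom no between-visit contact is described (enhanced usual care is itself not described), or coached participants in Weeks 17-24. An emergency visit without a two-week lapse in exercise could also escape the adherence check. The half-week figure needs an assumption about monitoring that Section 8.1 does not state.

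A second objection also stands as a caveat. The adverse-event list given to participants, the consent form and the Manual of Procedures are not in the documents available here, and any of them could carry an instruction to contact the study team. The finding is that the available text names no such route, not that none exists.

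**Conclusion.** The gap is real and worth closing. A single emergency event stops the study, but the available text gives no between-visit route or time limit for it to reach the study team. Where other contacts do not reveal the event, detection can wait on schedule up to 12 weeks for controls and up to 8 weeks for coached participants after Week 16. For opt-outs it can wait up to 12 weeks, but only if adherence monitoring also misses the event. A missed visit could lengthen any of these.

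Three stronger readings are tempting and not supported:

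- *The rule cannot act at the speed the plan states.* Section 8.3.5 states no speed for stopping. The immediacy there belongs to the report to the IRB. What is missing is a route; no stated deadline is contradicted.
- *Events will be learned six weeks late on average.* That is the visits-only scenario with uniform event times, not an expectation for the trial.
- *About seven others would go on exercising.* That number needs even accrual over 18 months and N = 25. Under other assumptions it is about 11 to 15, and about half would be controls. The conclusion does not depend on it.

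**What to change.** Leave the stopping rule to the sponsor. Reconcile Sections 1.3, 2.3.3, 6.1.1, 8.1, 8.3.2, 8.3.4 and 8.3.5 so that the route to the rule is explicit:

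1. In Section 2.3.3 and on the adverse-event list shared with all participants, in both arms, add that after contacting the provider or EMS the participant or other adult also notifies the study team, within a period the sponsor fixes.
2. In Section 8.3.4, replace the placeholder with the role that receives and records these reports.
3. In Section 6.1.1, have coaches forward any event they learn of the same day.
4. Because coach contact exists in one arm only, describe any adverse-event counts by arm with that difference in ascertainment stated. Section 9.4.4 currently marks safety analyses as not applicable.

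A periodic automated adverse-event check in both arms is optional. It would even out ascertainment, but it is a new procedure that needs building and someone to triage replies. A coach question without a counterpart for controls would widen the difference between arms.

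Items 1 to 3 cost a line on an existing handout, one role to name and a forwarding duty. The downside is slightly more minor events to log.
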